ORGANIZATION AND ACCESS TO RESEARCH DATA: With the exception of one server, named the "CCDOR Server," only the CCDOR Statistical & Data Management Team has access to remaining Center servers. Data on the "CCDOR Server" are organized by projects within folders designated by each investigator. Only members of a given project have access to a specific project folder on the "CCDOR Server." Even then, access to project data is obtained through Windows authentication (i.e., user's name and password to the network). It is virtually impossible for any person without a login name and password to the VA hospital's domain network to access data on the Center's servers. Thus, all data housed on the "CCDOR Server" are extremely secure, and access by unauthorized persons highly unlikely. Data containing patient identifying information are not stored on the CCDOR Server but are stored on the servers accessible only to CCDOR Statistical & Data Management Team members who are directly involved in the project. Thus, not even the PI can link individual names to their PHI without first obtaining permission to do so from the Statistical & Data Management Team. These protections exceed the usual protections provided PHI by the VA system.

SECURING CONFIDENTIAL RESEARCH DATA: Data collected for individual Center projects are often obtained through primary (e.g., surveys) or secondary (e.g., VISTA and Austin databases) sources. All extractions of secondary data collection are stored on servers accessible to the CCDOR Statistical & Data Management Team only. Secondary data used for a study are de-identified according to HIPAA criteria and provided a random study identification number. A crosswalk table is created linking the study id with the primary key of the secondary data source. These data are only accessible to those employees of the Statistical & Data Management Team who have undergone the necessary security background checks, received appropriate security clearances, and are an integral part of an IRB-approved study. Primary data that involves surveys contain only the coded study identification number to identify study participants. The paper version of these forms/surveys is kept in locked cabinets within a locked room. Data from these surveys/forms are scanned or data entered by project staff or CCDOR Statistical & Data Management Team members to a secure folder. This secure folder is on a server accessible only to the CCDOR Statistical & Data Management Team members directly involved in the study. This protects the integrity of the data as well as its confidentiality. Primary data collection involving direct data entry is performed through a custom application written by a CCDOR Statistical & Data Management Team programmer. This ensures that data is in a secure environment and accessible to only those individuals with permission to access the data. Only individuals with a need to access the data, as vetted by the project's Principal Investigator are granted access. Even then, only the absolute minimum number of data elements is released.

E.3. Data Used for Analysis:

For all projects conducted in CCDOR, the final data is constructed in Statistical Analysis Software (SAS) data sets. Analyses are mostly conducted by statisticians assigned to the project or by other members of the project (e.g. Principal Investigators). All data collected are stored in individualized SAS data sets pertaining to the specific type of analyses to be performed. These SAS data sets will be de-identified according to HIPAA criteria, using only subjects' coded identification number as the primary key. The de-identified data set will be made accessible to those project members who are conducting analyses. Only the data elements required for the analysis under consideration are released. In summary, a separate workspace on a server accessible only to project Statistical & Data Management Team members will be created to work with administrative data. Any of the administrative data containing patient level data will be encrypted when not being used by a project programmer. All patient-identifying information will be removed from the administrative records. Upon completion of all study data, de-identified analysis data sets will be created in SAS that will use the subjects' coded study identification numbers as the only key.

E.4. Transcriptions

We will use Keystrokes Transcription services to obtain transcriptions of patient recorded interviews. Recorded individual patient interviews will be identified only by a coded facility identification number. Interviews will be conducted by telephone and will be recorded directly to a password protected project file on a center server. Recordings will be transferred using a secure portal (Reflection FTP Client) to the identified transcription company (Keystrokes). Once recordings have been transcribed, the recordings will be deleted by the transcription company.

For all projects conducted in CCDOR, the final quantitative data is constructed in Statistical Analysis Software (SAS) data sets. Qualitative data includes audio recordings of interviews that are transcribed and then stripped of all identifiers. De-identified transcripts are then coded by study staff and/or uploaded into qualitative analysis software (NVIVO). Quantitative analyses are mostly conducted by statisticians assigned to the project or by other members of the project (e.g. Principal Investigator or Project Manager). Qualitative analyses are conducted by study investigators with qualitative expertise. All data sets and qualitative transcripts will be de-identified according to HIPAA criteria, using only subjects' coded identification number as the primary key. The de-identified data set will be made accessible to those project members who are conducting analyses. Only the data elements required for the analysis under consideration are released.

5.6F. Inclusion of Women and Minorities.

Women and minorities will be represented in our study sample. Any patient who enters the Minneapolis, Ann Arbor, or Atlanta outpatient PCT clinics during the study period and meets inclusion criteria will be eligible for participation regardless of gender or race.

5.6G. Inclusion of Children.

All study subjects are expected to be 18 years of age or older.

5.7 Recruitment Methods

5.7A. Study Setting

The study will be based in the Center for Chronic Disease Outcomes Research (CCDOR). All data collection will take place at the Minneapolis VAHCS.

5.7B. Recruitment Training

Given the importance of recruitment to the success of any study, staff will be trained in established best-methods for recruiting for behavioral intervention trials (e.g., Leonard, Lester, Rotheram-Borus, Mattes, Gwadz, & Ferns, 2003). Staff will know how to handle difficult situations while maintaining boundaries, establish and maintain rapport while not antagonizing or alienating participants, and handling reports of IPV or other risk issues. Regular recruitment supervision meetings will occur. Given the importance of establishing rapport to successful participant recruitment¹⁰⁷ and plans for careful training and supervision, staff will be trained in the use of scripts as guides to avoid impersonal or alienating recitation of scripts. Reading scripts verbatim may interfere with establishing rapport, adaptive social norms that promote asking questions, and a safe environment for individuals share when they do not understand or have concerns about the study. See Study Materials for example scripts.

5.7C. Referral Sources.

We will rely on three methods of identifying potentially eligible Veterans: 1) provider referral, 2) self-referral, and 3) identification from hospital records.

Provider Referral. Provider referral will provide our first-line recruitment source, as this will mirror how the intervention is delivered in typical clinic care. We will make announcements about the study in multiple settings and forums (e.g., announcements at team meetings, presentations at grand rounds). We will provide flyers and brochures to providers and discuss the study with them to inform them about the study. As providers and patients/significant others (e.g., caregivers) may prefer to discuss the study together, prior to referring the patient/caregiver to our team, fliers and brochures will assist in these efforts. Providers may or may not choose to discuss the study with the Veteran or caregiver first. We will then receive contact information for potentially eligible participant (i.e., veterans interested in PTSD care or trauma-focused treatments; caregivers with trauma-related mental health concerns) by (1) providers or by (2) team-leads in specialty clinics notifying study staff as patients are referred for evidence based PTSD treatment. Study staff will be provided with the potential participant's contact information through secure email, verbally, or through a cosigned CPRS note that an individual is interested in trauma-focused care (with subsequent communication verbally or through secure messaging).

Self-Referral. To facilitate self-referral, we will use study fliers and brochures strategically placed in appropriate clinic locations and make announcements to inform others about the study. We will also distribute fliers and brochures, make announcements, and provide presentations to community organizations to facilitate self-referral. Individuals who are self-referred to the study will reach out to study staff to express their interest directly. We will also distribute study fliers and brochures through social media groups and listservs (e.g., Facebook groups for veterans, emails to community groups). If potentially interested participants reach out to us via email, we will respond back thanking them for their email and interest in the study and asking them to talk by phone to protect their privacy. Distributing advertisements through social media and electronically is especially important given the ongoing pandemic.

Identification from Hospital Records. If approaches self and provider referral prove insufficient to reach recruitment goals, we will identify potentially eligible Veterans who have a diagnosis of PTSD through an administrative data pull and recruit these Veterans through the mail and telephone, using the same methods employed for provider referral participants.

5.7D. Recruitment Processes

Provider Referral.

Referral sources (e.g. providers) can talk about the study with their patients, their significant others/caregivers and provide them with a study brochure detailing the project. During this time, providers will ask if the individual is interested in being contacted about a research study for PTSD. This will give the individual an opt out option. If the individual responds "no", clinic staff will not contact study staff members. If the individual responds "yes" and would like to be called regarding a research study, the provider/staff will notify study staff. When a provider or off-team staff member refers an individual who has expressed an interest in being called regarding a research study, study staff will mail the individual information about the study and call the individual as soon as possible to give them information about the study.. This eliminates a delay in getting couples into care and follows the current clinic mandates regarding minimum

wait times for evidence-based treatment for PTSD. Off-team individuals will not make any efforts to recruit the individual and will refer the individual to study staff with any questions.

Alternatively, individuals' who have not been asked if study staff can contact them will be sent a letter in the mail and brochure about the study, informing them they will be contacted and how to decline study recruitment efforts. In this case, staff will attempt to reach the individual 7 days after the letter is sent.

Prior to initiating contact with the individual, study staff will review the veteran's hospital records to determine the presence of any study exclusionary criteria (e.g., the patient is currently hospitalized for a psychiatric emergency or reporting active psychotic symptoms).

Individuals will then be contacted by telephone by a trained interviewer to discuss the study and for initial screening. We will make up to 3 calls a week for 3 weeks, unless the individual declines recruitment or requests an alternative schedule (e.g., if he/she asks us to call more often to try to catch them at a time when they aren't busy or are somewhere in private). We will leave up to one message per week, unless the individual requests no voicemails or requests an alternative schedule. See Materials for an example voicemail script.

Upon contact with the individual, with their permission, a trained interviewer will then discuss the study and complete an initial screening, including for the presence of a significant other with whom they have been in a relationship with for at least 6 months, willingness to include the LO in treatment, presence of moderate intimate partner violence (SF CTS-2), and (for veterans) the presence of symptoms of PTSD on the PC-PTSD-5 (see inclusion/exclusion criteria for further detail).

The study procedures (assessment data gathering, intervention, session recording) and study design (including the nature of randomization to condition) will be fully described to the participant at the time of the initial contact (and again at the time that consent is documented). See script for initial screening call in Materials. For interested and eligible individuals, we will begin recruitment efforts for their significant other and begin or schedule the over-the-phone informed consent meeting with the significant other to complete enrollment.

For individuals who have expressed interest in the study (i.e., study staff spoke with them over the phone, completed screener, and/or completed informed consent), if at any time during the recruitment process study staff are unable to reach them, we will send them one final letter. The letter will inform the participant that we have been unable to reach them and that without contact within 2 weeks, we will have to close their case from our study records. The letter informs the individuals that we will no longer attempt to contact them and gives them the opportunity to reach out to study staff if they still have interest in participation in the study.

Self-referral and Referral through Identification from Hospital Records.

Procedures will follow the same general process as above with a few exceptions. For self-referrals, these individuals will be contacting study staff first, so we will immediately initiate

efforts to return their calls while also sending them an introductory letter and study brochure. See Materials for Introductory Letter.

For individuals identified through hospital records, the volume of mailings anticipated makes individual review of patients' records prior to their initial mailing impractical, so this component of the process will not take place prior to mailing for individuals referred through this channel. Additionally, as these individuals are not necessarily seeking treatment, we will wait 7 days after the initial mailing before attempting to contact them by telephone.

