Methods: To accomplish Aim 1, we will expand the outline for the intervention into an initial treatment manual through meetings with content experts and stakeholder feedback. Next, we will develop fidelity checklists and revise the treatment manual through conducting the intervention with 2-3 couples. To accomplish Aims 2 and 3, we will evaluate the intervention in a non-randomized, open trial with 12 veterans diagnosed with PTSD and their loved ones. Veterans will complete baseline and posttreatment structured diagnostic interviews. Both members of the couple will complete baseline surveys, surveys during treatment, posttreatment surveys, and posttreatment qualitative exit interviews. Using data obtained from the open trial, we will assess the intervention's acceptability, feasibility, mechanisms, and outcomes. Upon completion of this proposal, we will be well positioned to apply for Merit funding for a randomized clinical trial (Stage 2 of the Stage Model of Treatment Development) of this innovative, exposure based, couple therapy.

List of Abbreviations, Acronyms, and Symbols

BFT	Behavioral Family Therapy
CAPS-5	Clinician-Administered PTSD Scale for DSM-5
CCDOR	Center for Care Delivery & Outcomes Research
CES	Credibility Expectancy Scale
CE	Studio Community Engagement Studio
Co-I	Co-Investigator
COACH	Teaching Loved Ones to Help Veterans Optimize their PTSD Care and Healing
CPT	Cognitive Processing Therapy
CSQ-8	Client Evaluation of Services Questionnaire
DSM-5	Diagnostic and Statistical Manual of Mental Disorders
DoD	Department of Defense
EBP	Evidence Based Psychotherapy
FES	Family Environment Scale
HSR&D	Health Services Research and Development
HW	Homework
IPF	Inventory of Psychological Functioning
IIR	Investigator-Initiated Research
IRB	Institutional Review Board
ICBT	Integrative Behavioral Couples Therapy
LO	Loved Ones
MI	Motivational Interviewing
MH	Mental Health
N/A	Not Applicable
OCD	Obsessive Compulsive Disorder
OEF	Operation Enduring Freedom
OIF	Operation Iraqi Freedom
OMHS	Office of Mental Health Services
PEAS	Patient Exposure and Response Prevention Adherence Scale
PCL	Posttraumatic Stress Disorder Checklist (DSM-IV)
PCL-5	Posttraumatic Stress Disorder Checklist (DSM-5)
PE	Prolonged Exposure
PHQ-9	Patient Health Questionnaire
PI	Principal Investigator
PTSD	Posttraumatic Stress Disorder
RCT	Randomized Controlled Trial
SCID-5-CT	Clinical Trials Version of the Structured Clinical Interview for DSM-5
VA	Veterans Affairs

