5.0 Study Procedures

5.1 Study Design

First, we will expand the treatment outline for COACH (see Appendix 1) into an initial treatment manual through meetings with content experts and stakeholder feedback. Next, we will develop fidelity checklists and revise the treatment manual through a "test run" with 2-3 couples. The resultant intervention will then be evaluated in an open trial with 12 veterans diagnosed with PTSD and their loved ones. During the course of the open trial, we will refine fidelity checklists and develop a provider training program. Using data obtained from the open trial, we will assess the intervention's acceptability, feasibility,⁴⁴ mechanisms, and outcomes. Lastly, using clinical observations, participant feedback from qualitative exit interviews, and additional stakeholder feedback, we will make final edits to the manual, yielding a manual suitable for a future RCT (Stage II Manual).²⁵ Upon completion of this proposal, we will be well positioned to apply for Merit funding for a randomized controlled efficacy trial.²⁵

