Loved ones will be sent a letter and brochure describing the study, an informed consent form, and a HIPAA authorization form. The letter will inform them that they will be contacted and how to decline study recruitment efforts. They will then be contacted by telephone by a trained interviewer to discuss the study, their interest, and assess the presence of severe relationship violence. The study procedures (assessment data gathering, intervention, audio/videotaping) will be fully described to the participant at the time of the initial phone call. Participants will be informed of the study design (including randomization to condition) before they decide to participate. If the participant agrees to take part in the study, they will sign the informed consent form and HIPAA authorization by hand or electronically via Docusign. If signed by hand, the participant will mail the form back to study staff. All signed forms will be kept locked in staff file cabinets in a locked office. When signed electronically using Docusign, staff can access the signed form in the online Docusign sharepoint space and will export the document to study files.

If Veterans are deemed ineligible due to inclusion/exclusion criteria or lack of interest, LOs will be informed that full inclusion/exclusion criteria were not met for the Veteran and thus the dyad is no longer eligible for enrollment. Specific details on which inclusion/exclusion criteria (including level of interest in the study) will not be disclosed. The same approach will be used for LOs who decline participation or report severe relationship aggression (i.e., Veterans will be informed that full inclusion/exclusion criteria were not met for the Veteran and thus the dyad is no longer eligible for enrollment). Appropriate alternative referrals to mental health treatment, including substance use treatment or psychotherapy, or to address relationship aggression will be made as upon request and when clinically indicated (i.e., positive screens for psychosis, substance use, suicidality, homicidally, etc.).

5.8C. Retaking Baseline Assessments

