Relationship violence will be assessed by telephone from both Veteran and LO-report (Item 13). We will exclude Veteran participants if he/she has an underlying medical condition or a medical procedure (item 15 and 16) planned that would greatly impair their ability to participate in a weekly psychotherapy (i.e., a severe seizure disorder making weekly attendance difficult or a planned major surgery within a month of beginning treatment). This item will be assessed during the initial phone screening. Items 3, 4, 8, and 14 will also be assessed by phone screen. See materials document for screening items. We will administer a PTSD screen including the PCL-5, PHQ9, and questions regarding prior hospitalizations for MH concern, by telephone. If the loved one has (1) a PCL score above a 32, (2) a PHQ9 score of 9 or 10, and (3) they have ever had a hospitalization for MH or SUD concerns, a further case review will be conducted by a psychologist on the team. LOs and Veterans will be required to complete a baseline survey assessment before they can be randomized to a study arm. Failure to complete the baseline survey will result in study ineligibility (item 18).

We will exclude dyads in which either the Veteran or LO report moderate relationship violence (item 12), defined as one or more episodes of severe violence in the past year (e.g., kicked or beat up) on the IPSVS Adapted Scale¹⁰⁶. It would be counter-indicated for providers to proceed with PTSD treatment, without addressing ongoing significant relationship violence first. This is similar to the requirement that the patient must not be actively psychotic, manic, suicidal, or dependent on substances. Consequently, the reporting dyad member(s) will be provided with resources and referrals for IPV (see IPV risk algorithm). The dyad may be re-evaluated for eligibility when this exclusionary criteria has been resolved (i.e., one year has passed without an episode of severe violence). Finally, we can delay or end treatment, when clinically indicated, based on case review. For example, if the veteran is new to mental health care at the Minneapolis VA and

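### Sections 5.7D, 5.8B and 5.9 refer to randomization, and the first two tell candidates about it, although this is a one-condition, non-randomized open trial

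*Combined protocol and SAP*

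**What the plan says.** The design is stated in the Abstract (Methods): "we will evaluate the intervention in a non-randomized, open trial with 12 veterans diagnosed with PTSD and their loved ones". Section 5.1 agrees: "The resultant intervention will then be evaluated in an open trial with 12 veterans diagnosed with PTSD and their loved ones". It places a randomized trial in a later funding application. Section 5.4 acknowledges that there is no comparator and explains that adding one was considered and rejected because of what it would do to the sample size.

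Three later sections read differently:

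- Section 5.7D, on the first screening call: the "study design (including the nature of randomization to condition) will be fully described to the participant at the time of the initial contact". A parenthesis in the same sentence adds a second occasion, when consent is recorded. For self-referrals and people found through hospital records, the same section says "Procedures will follow the same general process as above with a few exceptions". Those exceptions concern mailings, record review and call timing, not the description of the design.
- Section 5.8B, on loved-one consent: "Participants will be informed of the study design (including randomization to condition) before they decide to participate".
- Section 5.9, on eligibility: "LOs and Veterans will be required to complete a baseline survey assessment before they can be randomized to a study arm".

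Section 5.8A, on veteran consent, does not mention randomization.

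**The concern.** Whether a couple will be assigned by chance or simply offered the study therapy is basic to the decision to take part, particularly for people seeking PTSD care. Sections 5.7D and 5.8B instruct staff to give candidates a description that does not match this trial, and to give it before they decide.

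There is also a smaller measurement issue. Section 6.1 lists the number of eligible veterans and loved ones who decline as administrative data on recruitment, and recruitment is one of the feasibility questions in Aim 2. If candidates were told that they might be randomized, that could influence who declined, and the count would then partly reflect a design the trial does not have.

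**Working it through.** No formula applies. The plan gives no alpha, power, effect size or allocation ratio, and the point rests on no figure in the plan. The check is a comparison of the sections.

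**1. How many conditions does the design have?** One.
- The Abstract describes the trial as non-randomized.
- Section 5.1 names COACH as the only intervention evaluated.
- Section 5.4 confirms that the absence of a comparator was deliberate.
- The timeline in section 5.5 has enrollment and treatment delivery but no randomization step.
- Section 7.2 plans descriptive summaries and pre-to-post change, with no between-arm comparison.

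**2. Is a second arm or an allocation method defined anywhere?** None was found in the supplied text.

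**3. Which sections presuppose randomization?** Three: 5.7D, 5.8B and 5.9. All are current protocol text, not entries in the amendment summary. Two of them (5.7D and 5.8B) govern what candidates are told. The third (5.9) governs the order of steps.

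**4. Who is covered?**
- Veterans are covered although 5.8A is silent, because 5.7D applies at first contact and again when consent is documented.
- Loved ones are covered by 5.8B.
- Self-referred people and those found through records are covered because 5.7D carries the same process over to them.

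**5. Could the wording mean that staff explain there is no randomization?** The 5.7D wording alone might be stretched that far. Sections 5.8B and 5.9 rule it out, since they treat allocation to a condition or an arm as something that happens.

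**6. What does the 5.9 step actually precede?**
- Section 5.8A puts veteran consent before any baseline measure, final eligibility after it, and then the first therapy appointment.
- For loved ones, 5.7D has staff "begin or schedule the over-the-phone informed consent meeting with the significant other to complete enrollment", and the baseline survey table in section 6.4 sends the survey link after consent is obtained.
- The step after the baseline survey and the eligibility decision is therefore the start of treatment, not randomization.

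**7. Scale.**
- Planned open-trial participants: 12 × 2 = 24, or 10 × 2 = 20 if the ten veterans in section 5.3A is the right figure.
- The test-run couples would add 2 × 2 = 4 to 3 × 2 = 6 people if they are additional and recruited in the same way, which the documents do not say.
- These are counts of participants, not of people exposed to the wording. The description is given at first contact, so people who later decline or screen out would hear it too. For orientation, section 5.3A reports 72 referrals for 18 randomized dyads in the related PE² study, or 72 / 18 = 4 referrals per dyad.

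**The case against.** The strongest reply is that harm has not been shown. What candidates hear depends mainly on the call script and the consent forms, neither of which was available here. Staff have no second arm or allocation method to describe. Section 5.8A has the consent material reviewed by telephone with veterans, with questions answered and comprehension checked. The wording looks carried over from another protocol: 5.3A says that PE² randomized dyads, and 5.6F names Ann Arbor and Atlanta clinics although 5.7A places all data collection at Minneapolis. On this view the defect is three stray phrases.

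Part of this stands. No one can be said to have been misinformed, and the participant counts do not measure exposure. Section 5.7B, which trains staff to use scripts as guides, is about rapport. It means that a correct script may not fix every word spoken, but it does not license staff to change the content, so little weight should rest on it.

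The rest does not remove the contradiction. Section 5.8B has explicit randomization wording and no comprehension check to match the one in 5.8A. The suggested origin is an inference, and wording left over from another study is still the instruction in force. Section 10.0 commits the team to conducting the study according to the approved protocol.

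**Conclusion.** The concern holds, with high confidence. Three current sections presuppose randomization in a trial with one condition, and following two of them exactly would give candidates a wrong account of the design before they decide. It should be corrected.

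The conclusion rests only on the protocol text. Calling the trial single-arm is an inference, though a direct one, from a non-randomized open trial with no comparator. The consequence is confined to the accuracy of recruitment and consent information, with a possible minor effect on how the decliner count is read. The sample size and the descriptive analysis do not change.

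**What to change.** - **5.7D and 5.8B:** delete the references to randomization. State that the study has one condition, that couples found eligible after the baseline assessments are offered COACH (subject to the case review already described in 5.9), and that there is no comparison group.
- **5.9:** replace the clause about being randomized with one saying that the baseline survey must be completed before study treatment begins. This matches the order of steps in 5.7D, 5.8A and 6.4.
- **Script and consent forms:** check that they match the corrected text.
- **If the randomization wording has already been used with candidates:** say so in one sentence where recruitment and decliners are reported, and consider whether it falls under the IRB reporting route in section 8.0.

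The cost is a short wording amendment to three sections and a check of the script and forms. The sample, the analysis and the clinical rules are unchanged.
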